15.1.4 Diagnostic accuracy

Crosstabulations of the results of each test will be reported (positive/negative/indeterminate). Sensitivities and specificities will be calculated for each test using the numbers of lung cancer cases or non-cases respectively and reported together with appropriate 95% confidence intervals.

15.1.5 Imaging logistics

The proportions of recruited participants not undergoing imaging with CXR alone, LDCT alone and both CXR and LDCT will be reported together with appropriate 95% confidence intervals.

15.1.6 Clinical outcomes

An estimate of the prevalence of lung cancer in the MEDLEY study population will be reported as a percentage together with an appropriately derived 95% confidence interval. The prevalence will be estimated based on confirmed cancer diagnoses after 12 months of follow-up.

15.1.7 Risk stratification strategy

The strategy developed by the MEDLEY team [27] will be reviewed using the MEDLEY study data. Incidence of lung cancer will initially be investigated according to the age and smoking status of MEDLEY participants. Comparisons between the data observed in MEDLEY will be drawn with data from the initial development of the risk strategy.

15.2 Sample Size

Based on realistically recruiting 5 participants per site per week (i.e. 20 per site per month) and allowing staggered opening of sites, it is estimated that 900 participants can be recruited to MEDLEY within a 12-month recruitment timeframe. Recruiting a total of 900 patients will permit estimation of a per-centre-month recruitment rate for a full diagnostic accuracy trial and relevant trial sample size parameters with acceptable precision. For the recruitment rate, using generalised linear modelling theory, and working with the log-likelihood and Hessian for a one-parameter Poisson model, 900 participants gives a 2-sided 95% confidence interval for relative precision as (1/1.068 to 1.068) times the estimated rate. For example, with 20 participants per centre-month recruited, then a 95% confidence interval for the true recruitment rate would be (18.7 to 21.4) per centre-month. Based on 2021/22 -level data, between 250-579 CXRs per week per site are requested [25]. Our unpublished analysis indicates 31% of CXRs fulfil NG12 criteria, and experience with the Yorkshire Lung Screening Trial demonstrates 50% of eligible patients are recruited. Hence the average recruitment rate of five/week/centre is realistic.

Sensitivities of CXR and LDCT will be estimated. We anticipate that prevalence of lung cancer detected will be at least 1.7%. This is based on the proportion of those who were diagnosed with lung cancer within two years following investigation with CXR and with similar characteristics as participants who will be recruited to MEDLEY [40]. Although the follow up period for MEDLEY will be one year, rather than two years, the number of cancers detected will exceed that which would be identified on CXR alone and it is likely that a substantial proportion of cancers not detected on CXR would take longer than two years to be diagnosed [41].

As a feasibility study, MEDLEY has not been designed for any pre-specified precision (which would be the design criteria for a definitive trial). With a prevalence estimated as 1.7%, an estimated sensitivity of 90% would have an 95% exact confidence interval covering values as low as 72% (estimated using the Clopper-Pearson exact method). Other metrics including specificity of CXR/LDCT, proportions of concordant/discordant imaging results, proportions completing imaging, and proportions completing questionnaires would all have 2-sided 95% confidence intervals +/- 3.3% (estimated using the normal approximation method) assuming that a minimum of 97% of participants are included in estimates of specificity, and assuming a worst-case estimate of 50% where estimated variance is maximised.

We have used simulation to predict how precisely we will estimate the proportion of CXR requests that fulfil NG12 criteria. Assuming that there will be at least 169 centre-weeks of recruitment and that for each of these, GP CXR requests will be assessed for NG12 and those eligible contacted until 5 potential recruits are identified, we expect to estimate the proportion of requests fulfilling NG12 with a 95% confidence interval width of 2.4%, with the interval width being below 3.0% with 90%

probability. The simulation incorporated uncertainty in the population proportion of CXR requests fulfilling NG12 criteria (Beta distribution with parameters 31 and 69) and the proportion of CXR requests which do fulfil NG12 criteria resulting in a potential recruit (Beta distribution with parameters 5 and 5).

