8.1. WP1

WP1 aims to recruit 900 participants with symptoms that may suggest lung cancer who have been referred from primary care for CXR from at least five UK centres. Patients will be recruited from secondary care sites and will follow a standard care pathway. All patients will receive a LDCT as well as a CXR, and both LDCT and CXR will be reported by independent consultant radiologists. The LDCT will be used to guide clinical care by the secondary care team and the report will be sent to the referring GP. All participants will be followed up for a maximum of 52 weeks. Outcomes are defined in section 14 grouped as i) feasibility of deliverability; ii) qualitative acceptability; iii) estimates of diagnostic accuracy; iv) imaging logistics; v) clinical outcomes; vi) economic outcomes. Those outcome measures informing the decision criteria to progress to definitive trial are stated in sections 14.1 and 14.2. The reference standard will be cancer diagnosis within 12-months of clinical follow-

up, but cancer diagnoses resulting from the paired LDCT (i.e. MDT approved diagnosis within 3 months of LDCT) will also be reported as a contemporaneous reference standard.

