15.1.3 Feasibility outcomes

The monthly recruitment rate of participants to the study will be calculated by centre and overall. Point and precision estimates will be obtained for the recruitment rate using a log-linear Poisson regression model, with an offset term for total recruitment duration.

The number of participants who consent and who do not consent to participate in MEDLEY will each be divided by the number of patients screened who are eligible to take part in the study. A confidence interval for the proportion will be calculated using the exact method.

Centre performance will be summarised descriptively:

- Time from site approach (defined as date of issuing formal site selection email) to opening (defined as date of Sponsor Green Light to recruit email)
- Time from site opening to recruiting first participant
- Duration of site recruitment

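### The recruitment-rate interval in 15.2 describes the participating centres only; offered as the precision for a full trial, it omits between-centre variation from as few as five centres

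*Protocol*

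**What the plan says.** Section 15.2 (Sample Size) sets out the purpose: "Recruiting a total of 900 patients will permit estimation of a per-centre-month recruitment rate for a full diagnostic accuracy trial", with precision described as acceptable. The supporting figure is put this way: "working with the log-likelihood and Hessian for a one-parameter Poisson model, 900 participants gives a 2-sided 95% confidence interval for relative precision", the interval being a factor of 1/1.068 to 1.068. The worked example is that "with 20 participants per centre-month recruited, then a 95% confidence interval for the true recruitment rate would be (18.7 to 21.4) per centre-month".

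Section 15.1.3 (Feasibility outcomes) plans to calculate the monthly rate by centre and overall. Point and precision estimates are to be obtained "using a log-linear Poisson regression model, with an offset term for total recruitment duration". Neither section mentions a centre effect or an overdispersion term.

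Section 8.1 plans to recruit patients "referred from primary care for CXR from at least five UK centres". The number of centres plays no part in the interval in 15.2.

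Recruitment rate per centre-month is the first starred outcome in 14.1.1. Starred outcomes are those that inform the decision to proceed to a definitive trial, or its design.

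**The concern.** An interval that depends only on the total recruited would be the same whether the 900 came from one centre or from fifty. That suits the question of how fast these centres recruited on average. It does not suit the question that 15.2 says it answers, which is the rate to plan on in a full trial. Such a trial would run in other or additional centres. For that target the centre is the sampling unit, and there may be only five.

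What is at stake is how the result is read. A definitive trial's number of centres and recruitment period follow from this rate. If the interval is taken at face value, the planning range looks narrower than five centres can support whenever centres differ.

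**Working it through.** **Inputs.** From the protocol: 900 participants, a two-sided 95% interval and an example rate of 20 per centre-month (15.2), and at least five centres (8.1). Not in the protocol: the between-centre CV of recruitment rates. It is assumed here at 0.1, 0.2 and 0.3. Equal time open per centre is also assumed: 900/20 = 45 centre-months, or 9 per centre.

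**Step 1: reproduce the stated figure.** In a one-parameter Poisson model, Var(log rate) = 1/900, so the standard error is 1/30 = 0.0333. The factor is exp(1.96/30) = 1.0675. Then 20/1.0675 = 18.7 and 20 × 1.0675 = 21.4. The exact Poisson interval for 900 events in 45 centre-months is 18.71 to 21.35. The plan's figure is correct for its model.

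**Step 2: add between-centre variation.** With k centres of equal exposure,

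Var(log rate) = 1/900 + ln(1 + CV²)/k.

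For k = 5 and CV = 0.2: ln(1.04)/5 = 0.00784, against 1/900 = 0.00111. The sum is 0.00896 and the standard error is 0.0946. With the normal quantile, exp(1.96 × 0.0946) = 1.204, giving 16.6 to 24.1. With t on 4 df (2.776), exp(2.776 × 0.0946) = 1.300, giving 15.4 to 26.0.

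The ratio columns compare the log-scale half-width with the stated one (1.96/30 = 0.0653).

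| Assumed CV | Normal quantile | Ratio | t, 4 df | Ratio |
|---|---|---|---|---|
| 0.1 | 17.9-22.3 | 1.7 | 17.1-23.3 | 2.4 |
| 0.2 | 16.6-24.1 | 2.8 | 15.4-26.0 | 4.0 |
| 0.3 | 15.3-26.1 | 4.1 | 13.7-29.1 | 5.8 |

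The normal-quantile column treats the CV as known. The t column allows for its being estimated from five centres, and part of its extra width comes from the multiplier alone (2.776/1.96 = 1.42).

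**Step 3: sensitivity.** At CV 0.05 the ratio is only 1.2 (normal) or 1.7 (t). On the normal scale it reaches 2 at a CV of about 0.13 and 3 at about 0.21. Five centres is a minimum. With ten centres and CV 0.2 the interval is 17.4-23.0 (normal) or 17.0-23.5 (t, 9 df).

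**Step 4: coverage.** In a simulation with five centres, gamma-distributed centre rates averaging 20 and 100,000 runs per setting, the Poisson interval covered as follows.

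| Assumed CV | Covers the participating centres' own average | Covers the mean over the wider population of centres |
|---|---|---|
| 0.1 | 95% | 76% |
| 0.2 | 95% | 50% |
| 0.3 | 95% | 36% |

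The shortfall therefore lies in the target to which the interval is applied, not in its derivation.

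**The case against.** Several points on the other side are sound.

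- **The interval does not require equal centre rates.** A reader might infer that a one-parameter Poisson model is valid only if every centre recruits at the same rate. That is not so. A sum of independent Poisson counts with unequal rates is still Poisson, and the 95% coverage in Step 4 confirms that the interval holds for the participating centres' average.
- **The protocol does not show that recruitment rates differ between centres.** A reader might take the statement that "between 250-579 CXRs per week per site are requested" as a 2.3-fold spread in recruitment. It is a spread in referral volume. On the protocol's own figures the smallest site yields 250 × 0.31 × 0.5 = 39 potential recruits a week, against five sought, so volume is not the limit. A common weekly target could even bring centre rates together. The pilot table in 8.4 gives decision cut-offs at 50% and 100% of one target, not a range of centre rates.
- **An unconditional claim that the interval is several times too narrow is not supported.** It depends on a CV that the protocol does not state, and at CV 0.1 or below the normal-scale factor is under 2.
- **The sample size does not rest on this interval.** Section 15.2 bases 900 on what can be recruited in 12 months, and says the study has no pre-specified precision.
- **Centre rates will be visible, and a SAP will follow.** Section 15.1.3 reports rates by centre, and the SAP could add a centre term.

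The first four limit how the point may be put, but they do not remove it. Declaring no precision target does not cure a specific figure offered as acceptable precision for a full trial. On the last, listing centre rates does not widen the overall interval. Section 15.1.3 names the model and its offset without a centre term, and a later SAP would leave the figure in 15.2 as it stands. Capacity may limit recruitment instead of volume, and 12.10 says it depends on several site factors. Variation between centres therefore remains possible, though unmeasured.

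**Conclusion.** The point holds as a limit on what the interval describes. The figure of 18.7-21.4 is correctly calculated and valid for the average rate of the participating centres. It is not the precision of the rate for a definitive trial's centres unless between-centre variation is negligible, and 15.2 presents it as if it were.

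How much too narrow it is depends on an assumption. With five centres, equal exposure and a CV of 0.1 to 0.3, the half-width on the log scale would be about 1.7 to 4.1 times the stated one with a normal quantile, or 2.4 to 5.8 times with t on 4 df. A smaller CV or more centres would reduce this. The defect is an overstated precision claim for a starred outcome. It does not undermine the choice of 900 participants or the pilot progression criteria.

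**What to change.** **Section 15.1.3.** Keep the rates by centre. Estimate the overall rate with a method that allows for between-centre variation: either a t-interval on centre-level log rates, or a Poisson model with a log offset for time open and a centre random intercept. Add a prediction interval for a new centre, since that is the quantity a definitive trial needs.

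**Section 15.2.** State that 1/1.068 to 1.068 (18.7-21.4) applies to the average rate of the participating centres. Say that it carries over to a definitive trial's centres only if between-centre variation is negligible. Next to it give the wider interval for a stated CV, labelled as assumed; for example, 16.6-24.1 (normal) or 15.4-26.0 (t, 4 df) at CV 0.2 with five centres.

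**Cost.** A few sentences and slightly more analysis, using rates that are already to be calculated monthly by centre. The stated precision becomes less favourable. The between-centre variance will itself be imprecisely estimated from about five centres, and the report should say so.

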7.2. Primary Objectives

a) To undertake a feasibility study to establish the feasibility of a definitive trial based on the barriers and facilitators of a definitive trial, and to estimate parameters for the design of a potential, future definitive trial.

b) To obtain estimates of diagnostic accuracy of CXR and LDCT and establishing if these estimates are consistent with those from asymptomatic populations in RCT settings and symptomatic populations using retrospective data.

c) To undertake a model-based economic evaluation of changing the initial investigation for patients with suspected lung cancer from CXR to LDCT (either for all patients, or for a targeted subgroup of patients), and a value of information analysis with respect to a definitive trial.

d) To undertake an embedded qualitative study to obtain views on participation and nonparticipation, acceptability of trial design, recruitment and imaging requirements, and a stakeholder event to discuss implementation during and post-trial.

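### The 72% lower confidence limit for a sensitivity of 90% does not follow from 900 participants at 1.7% prevalence; those inputs give about 64%

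*Protocol*

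**What the plan says.** All the inputs stand in Section 15.2 of the protocol.

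- **Sample size.** The target is 900 participants, also given in Section 8.1. It is justified mainly by the recruitment rate: "Recruiting a total of 900 patients will permit estimation of a per-centre-month recruitment rate for a full diagnostic accuracy trial".
- **Prevalence.** "We anticipate that prevalence of lung cancer detected will be at least 1.7"%. The basis given is the proportion diagnosed within two years of a chest X-ray in a similar population.
- **Precision for sensitivity.** The claim is tied to that prevalence: "With a prevalence estimated as 1.7%, an estimated sensitivity of 90% would have an 95% exact confidence interval covering values as low as 72"%. The method is named: "estimated using the Clopper-Pearson exact method".

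The same paragraph says that no precision target was set in advance. It then gives a half-width of 3.3 percentage points for specificity and several other proportions.

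**The concern.** The sentence names its prevalence, estimate, method and result, so it can be checked completely. With about 15 cancers, an exact interval around 90% has to be very wide, and a lower limit of 72% looks too high.

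Sensitivity of CXR is one of the starred outcomes in Section 14.1.2, meaning that it informs the decision on a definitive trial or its design. Section 8.4 has the oversight committee review the sample size assumptions and report to the funder. A reader in either group would take from Section 15.2 that a sensitivity observed at 90% rules out values below 72%. If the true limit is lower, the study has been presented as more informative about sensitivity than it will be.

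**Working it through.** **Inputs.** N = 900, prevalence 1.7%, estimated sensitivity 90%, 95% Clopper-Pearson interval (all from Section 15.2). The sentence does not say whether the interval is one- or two-sided. The other intervals in that paragraph are two-sided, so two-sided is the natural reading.

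**Expected cancers.** n = 900 × 0.017 = 15.3.

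**Formula.** Lower limit L = BetaInv(0.025; x, n − x + 1), where x is the number of cancers detected.

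**Attempt to reproduce 72% from the stated inputs.** With x = 0.9 × 15.3 = 13.77 and n − x + 1 = 2.53, L = 64.0% (upper limit 99.2%). The stated figure is not reproduced.

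**Whole cancers.** No whole number out of 15 is exactly 90%, so the neighbouring values are shown.

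| Detected / cancers | Estimate | Two-sided 95% exact lower limit |
|---|---|---|
| 13/15 | 86.7% | 59.5% |
| 14/15 | 93.3% | 68.1% |
| 14/16 | 87.5% | 61.7% |
| 15/16 | 93.8% | 69.8% |

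None reaches 72%. If imaging is incomplete, the limit at 90% falls slightly further: 63.5% with 97% of the 900 analysed and 63.1% with 95%.

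**Other methods at 90% and n = 15.3.** A one-sided 95% exact bound gives 68.0%, Wilson 66.3% and Wald 75.0%. None gives 72%, and the protocol names the exact method.

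**What would give 72%.** Holding the estimate at 90%:

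- n = 26 gives 71.8% and n = 27 gives 72.3%.
- At 900 participants these are prevalences of 26/900 = 2.9% and 27/900 = 3.0%.
- At 1.7% prevalence they need 26/0.017 ≈ 1,529 and 27/0.017 ≈ 1,588 participants.
- Against the 15.3 expected, that is 26/15.3 = 1.70 to 27/15.3 = 1.76 times as many cancers.

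Rounding to whole cancers near 90%, the limit first comes to 72% at 21/23 (estimate 91.3%, limit 71.96%). That still means 23/900 = 2.6% prevalence.

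**Size of the discrepancy.** 72 − 64.0 = 8.0 points at exactly 90%; 72 − 68.05 = 3.95 points for 14/15; 72 − 59.54 = 12.46 points for 13/15.

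**Neighbouring figures, as a control.** The other precision figures in Section 15.2 do reproduce:

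- 1.96 × √(0.25/873) = 0.0332, the stated 3.3 points, with 873 = 0.97 × 900.
- exp(1.96/√900) = 1.0675, the stated 1.068. Then 20/1.0675 = 18.7 and 20 × 1.0675 = 21.4.

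**The case against.** **Prevalence is given as a minimum.** More cancers would raise the limit. However, the 72% sentence conditions on 1.7% itself, and the prevalence would have to reach about 3% for 72% to hold at 90%. This does not rescue the figure.

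**A one-sided bound for 14/15 is 72.1%.** It is the one exact-method route to 72% with 15 cancers. But 14/15 is an estimate of 93.3%, not 90%, and a one-sided bound is not the interval that the sentence describes.

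**The study disclaims any precision target.** This stands as a limit on the consequence. The 900 rests on recruitment, the pilot criteria in Section 8.4 do not use the 72%, and the economic model in Section 16.2 takes in the data MEDLEY collects, not this planning figure. It does not make a stated number correct.

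Three stronger inferences are tempting, and the protocol does not support them.

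- *That the 97% in the next sentence is a second error.* The text reads "assuming that a minimum of 97% of participants are included in estimates of specificity". At 1.7% prevalence 98.3% are non-cases, so a minimum of 97% is met, with 1.3 points left for incomplete imaging. The half-width is 3.3 points either way. Since 97% is the complement of 3%, both figures may come from a 3% prevalence, but the protocol does not say so.
- *That the accuracy results have no other stated precision.* Specificity, also listed as a primary WP1 measure in the study summary, has one.
- *That any CXR result would agree with the literature, so that objective 7.2(b) must be reworded.* That objective speaks of "establishing if these estimates are consistent with those from asymptomatic populations in RCT settings and symptomatic populations using retrospective data". With 15 cancers, 7/15 or fewer excludes 77% (upper limit 73.4% at 7/15), and 12/15 or more excludes 47% (lower limit 51.9% at 12/15). Discrimination is weak but not absent. The objective sets no test or threshold, and Section 15.1.4 already commits to estimates with 95% intervals. Rewording it is an editorial preference.

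**Conclusion.** Wrong as written. On the plan's own inputs the two-sided 95% Clopper-Pearson lower limit is about 64%, or 60% and 68% for 13/15 and 14/15. The stated precision for sensitivity is too favourable by about 8 percentage points (4 to 12).

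This rests on 15.3 expected cancers, a two-sided interval and no loss to incomplete imaging; allowing for such loss lowers the limit a little further. The actual number of cancers will vary around the expectation.

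The point is a should-fix, because no sample size, analysis or progression rule depends on the figure. It is worth correcting because the error runs in the favourable direction and the section is read by those who judge what the study can deliver.

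**What to change.** Do one of two things in Section 15.2.

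1. Replace 72% with about 64%. A clearer form gives whole cancers: *with 900 participants and 1.7% prevalence (about 15 cancers), an observed sensitivity of 13/15 or 14/15 has an exact two-sided 95% lower limit of 60% or 68%.*
2. If 72% is to stay, state the prevalence that yields it (about 3% at 900 participants), justify it, and reconcile it with the 1.7% given earlier in the section.

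The cost is a protocol text change and a less favourable stated figure. Recruitment, sample size, analyses and progression criteria stay as they are. The 97% assumption and objective 7.2(b) need no change on this account.

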6.3. The role for LDCT

Low-dose computed tomography (LDCT) produces more detailed images than CXR and exposes patients to less radiation than conventional CT. Although LDCT has been shown to be more accurate than CXR in asymptomatic patients [9] its accuracy compared to CXR in symptomatic patients is unknown [10]. LDCT scans take longer to acquire and interpret and are more expensive (£90 vs £27) than CXR [11]. LDCT is much more likely to lead to findings of incidental abnormalities, unrelated to patients' symptoms, or nodules which then require further tests and/or follow up, the majority of which are subsequently found to be benign [9, 12]. Such findings can lead to unnecessary anxiety and inconvenience for patients [13, 14]. The most robust comparison of LDCT and CXR is from a screening study in asymptomatic patients, undertaken in the US [9]. Sensitivities were determined with reference to cancers presenting within 12 months of each test. These were reported as 94% for LDCT (95% CI 91 to 96%) and 73% for CXR (95% CI 73 to 74). However, accounting for the additional cancers detected on LDCT which were probably present in the CXR arm at the time of screening but presented beyond the 12-month follow-up period, CXR sensitivity may be as low as 47% (136/284) even accounting for overdiagnosis [15]. A systematic review of CXR in symptomatic patients reported sensitivity between 77% and 80%, based on presentations of lung cancer within one year of the test [7]. This estimate will also be affected by cancers present at the time of the CXR but not presenting for several years [15]. As well as uncertainty about the difference in sensitivity between CT and CXR in symptomatic patients, there are no published data about the stage distribution of the cancers missed on CXR but that LDCT would detect (subsequently termed CT-extra cancers). Screening studies report increased proportions of early stage lung cancers detected by CT (70% stage I/II in NLST and 77% in NELSON) [9, 16]. However, the stage distribution of CT-extra cancers in symptomatic patients may be less favourable. Lung cancers that cause symptoms tend to be larger, and may be located in parts of the lung poorly evaluated on CXR (e.g. the central hilar regions). Tumour size and central location both predict earlier metastatic spread, so these symptomatic cancers that are

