14.1.2 Estimates of diagnostic accuracy

- To inform sample size calculation for a definitive trial:
 - (*) Sensitivity & specificity of CXR using contemporaneous LDCT as a reference standard
 - Comparative sensitivity and specificity of LDCT and CXR using lung cancer diagnoses within one year (given the shorter follow-up this being a feasibility study) as reference standard
 - Sensitivity of CXR reported by cancer stage using contemporaneous LDCT as a reference standard
 - (*) Correlation/discordance between LDCT and CXR test results: proportions of paired tests that agree/disagree on presence of lung cancer.

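### Section 15.2 illustrates the precision of sensitivity only at 90%, above every chest X-ray value the protocol cites, and the printed lower limit of 72% does not follow from the roughly 15 cancers expected

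*Protocol*

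**What the plan says.** Section 8.1 sets the size: "WP1 aims to recruit 900 participants with symptoms that may suggest lung cancer". Section 15.2 says this will allow estimation of a recruitment rate and of "relevant trial sample size parameters with acceptable precision". It adds that the sensitivities of both CXR and LDCT will be estimated, and gives the prevalence: "We anticipate that prevalence of lung cancer detected will be at least 1.7" per cent.

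The same section then says that, as a feasibility study, MEDLEY was not designed for any pre-specified precision. Its single illustration for sensitivity follows: "an estimated sensitivity of 90% would have an 95% exact confidence interval covering values as low as 72" per cent, by the Clopper-Pearson method. It does not name the test, the number of cancers or whether the limit is one- or two-sided. The other proportions listed next, including specificity and concordance, get two-sided intervals at a worst-case value of 50%.

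Section 14.1.2 stars one sensitivity outcome: "Sensitivity & specificity of CXR using contemporaneous LDCT as a reference standard". Test discordance (14.1.2) and prevalence (14.1.4) are starred too.

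Section 6.3 supplies the values to expect. The asymptomatic screening study reported 94% for LDCT and 73% for CXR. After adjustment for cancers presenting beyond 12 months, "CXR sensitivity may be as low as 47% (136/284) even accounting for overdiagnosis". For symptomatic patients: "A systematic review of CXR in symptomatic patients reported sensitivity between 77% and 80" per cent.

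**The concern.** The width of an exact interval depends on the number of cancers and on the assumed sensitivity. Section 15.2 appears to be off on both.

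- **Assumed value.** 90% is close to the LDCT figure of 94% and 10 points above the highest CXR figure cited. The sentence comes after a statement that both tests will be estimated, so a reader may apply it to CXR, which is the starred test.
- **Number of cancers.** The printed limit of 72% looks too high for about 15 cancers, whichever test is meant.

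The funder, the oversight committee and the designers of a definitive trial will read section 15.2 to judge how firmly CXR sensitivity will be known. CXR sensitivity is one of several starred inputs. A figure that is too favourable, in a section that claims acceptable precision, understates the uncertainty they would carry forward.

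**Working it through.** **Inputs.** N = 900 (8.1); prevalence 1.7%, stated as a minimum (15.2); sensitivity 90% with lower limit 72% (15.2); CXR values 47%, 73%, 77% and 80% (6.3).

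**Expected cancers.** 900 x 0.017 = 15.3.

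**Formula.** Two-sided 95% Clopper-Pearson for x detected among n cancers: lower = Beta quantile at 0.025 with parameters (x, n - x + 1); upper = Beta quantile at 0.975 with parameters (x + 1, n - x). Fractional x = p x n is allowed so that the stated percentages can be used directly.

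**Step 1: reproduce the 72%.** At n = 15.3 and p = 0.90 the interval is 64.0% to 99.2%, so 72% is not reproduced. The alternatives tried were:

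- 14/15 (93.3%): two-sided lower limit 68.1%.
- 13/15 (86.7%): two-sided lower limit 59.5%.
- 14/15, one-sided 95%: 72.1%. This matches the printed limit, but for an estimate of 93.3% rather than 90%, and the section uses two-sided intervals for the other metrics.
- Two-sided at 90%, varying n: 71.8% at n = 26, 72.3% at n = 27, 72.7% at n = 28.

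A two-sided limit of 72% at 90% therefore needs about 27 cancers, which is 27/900 = 3.0% prevalence rather than 1.7%.

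**Step 2: the protocol's own CXR values at n = 15.3.**

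| Sensitivity | 95% interval | Width (points) | Estimate minus lower limit (points) |
|---|---|---|---|
| 90% | 64.0-99.2% | 35 | 26.0 |
| 80% | 52.2-95.6% | 43 | 27.8 |
| 77% | 49.0-94.1% | 45 | 28.0 |
| 73% | 44.9-91.9% | 47 | 28.1 |
| 47% | 21.8-73.4% | 52 | 25.2 |

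The printed figures imply a distance of 90 - 72 = 18 points from estimate to lower limit. The calculated distance is 25-28 points at every value, including 90%.

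**Step 3: separate the two effects.** The shortfall in downward distance (18 against about 26 points at 90%) comes from the 72% not matching 15.3 cancers. Using 90% instead of a CXR value changes that distance by about 2 points at most. Its effect is on the total width, which is 35 points at 90% because the upper limit is near 100%, and 43-52 points at the CXR values.

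**Step 4: a larger number of cancers.** The prevalence is stated as a minimum. If it were doubled (an assumption), n = 30.6 and the intervals would be 62-92% at 80% and 29-66% at 47%, still 30 and 37 points wide.

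**The case against.** The strongest reply is that section 15.2 disclaims any precision target immediately before the sentence at issue, never labels the 72% as a CXR figure, and treats precision as a matter for the definitive trial. On that reading the 90% is only an example. This stands to the extent that no design criterion has been missed and nothing here calls for more participants. It does not rescue the 72%, which is a stated result that its own inputs do not give, nor the claim of acceptable precision earlier in the section.

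A second reply is that 47% and 73% come from asymptomatic screening and that 1.7% is a minimum. Both points are fair. With the symptomatic range of 77-80% alone, the interval still runs from 49% to 96%; doubling the cancers narrows it without making it tight.

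Three stronger readings are tempting but not supported:

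- **That the choice of 90% alone inflates the lower limit by tens of points.** Most of the movement between the 90% line and the CXR lines is the estimate itself moving. The downward distance hardly changes.
- **That CXR sensitivity is the parameter that sizes a definitive trial.** Discordance and prevalence are starred as well.
- **That objective 7.2(b), on "establishing if these estimates are consistent with those from asymptomatic populations in RCT settings", will be decided by overlap of wide intervals.** The protocol nowhere says that overlap will count as consistency. How it is judged is commonly left to the statistical analysis plan, which is not at hand.

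**Conclusion.** The point holds as a fault in a stated figure and in how it is illustrated, not as a flaw in the design. At 90% and 15.3 cancers the two-sided lower limit is about 64%, so the printed limit is about 8 points too high. The one sensitivity value illustrated lies above every CXR value cited, while the starred test would have intervals 43-52 points wide. A claim of acceptable precision for sample size parameters is therefore not supported for CXR sensitivity by anything shown in section 15.2.

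This rests on 900 participants all contributing, a prevalence of exactly 1.7%, a two-sided 95% interval, and the sensitivities in section 6.3. A higher prevalence narrows the intervals; missing imaging or follow-up widens them.

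**What to change.** In section 15.2:

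1. State the expected number of cancers (about 15, a floor because the prevalence is a stated minimum) and that the interval is two-sided.
2. Restate the 90% line as about 64-99% and label it as LDCT. If 72% was meant under other inputs, give them.
3. Add CXR intervals: about 49-94% at 77% and 52-96% at 80% as the symptomatic case and, as a lower scenario from asymptomatic screening, about 45-92% at 73% and 22-73% at 47%.
4. Limit the statement on acceptable precision to the parameters for which it holds, such as the recruitment rate, so that it agrees with the statement that no precision was pre-specified.

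The cost is a few sentences. No participants, data, procedures or analyses change. The only downside is that the stated precision looks less favourable.
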